In tables of severity, maximum severity observed for the parameter after dosing will be summarized. Tables of maximum severity for “Any Parameter” will be included for chemistry, hematology, and urinalysis laboratory results. In these tables, the maximum severity across all laboratory results in the respective category is summarized by visit, and from maximum severity post baseline. Ordinarily, only the maximum severity event will be counted in the summary tables. For instance, if subject has a mild decrease and a moderate increase observed post-dose, they will be counted once as a moderate increase for maximum severity post-baseline. In the exceptional case that a subject has an increase and a decrease of equal maximum severity, they will be counted twice for maximum severity post baseline, once for an increase and once for a decrease.

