9.7. Vital Signs and Physical Evaluations

VS measurements include systolic blood pressure, diastolic blood pressure, pulse rate, respiratory rate, and oral temperature. VS will be assessed within 60 min of dosing (baseline), 1 h (± 10 min), 2 h (± 10 min), and 4 h (± 10 min) after dosing, and at Day 2, Day 3, Day 4, and Day 8 or ET. VS will be tabulated by parameter, severity grading, and visit (Table 96, Table 97, Table 98, Table 99, Table 100, and Table 101) and listed (Listing 15). Additionally, descriptive statistics, including mean, standard deviation, median, minimum and maximum will be presented to summarize VS at baseline and post-dose and will also present change from baseline (Table 102, Table 103, Table 104, Table 105 and Table 106). For each vital sign, individual line plots showing the vital sign over time will be shown by parameter (Figure 28, Figure 29, Figure 30, Figure 31 and Figure 32). Subjects will not be labeled in the line plots, as the purpose of the figures is to give an overall trend of trajectory.

In tables of severity, maximum severity observed for the parameter after dosing will be summarized. Tables of maximum severity for “Any Parameter” will be included for VS results. In these tables, the maximum severity across all VS is summarized by visit, and from maximum severity post baseline. Ordinarily, only the maximum severity event will be counted in the summary tables. For instance, if subject has a mild decrease and a moderate increase observed post-dose, they will be counted once as a moderate increase for maximum severity post-baseline. In the exceptional case that a subject has an increase and a decrease of equal maximum severity, they will be counted twice for maximum severity post baseline, once for an increase and once for a decrease.

A complete physical examination (PE), except genital, rectal and breast exams, will be conducted at Screening and at Day 8 (± 2) or ET. This examination will assess general appearance, HEENT (head, eyes, ears, nose and throat), heart, lungs, abdomen, skin, musculoskeletal system, and lymph nodes, and include an abbreviated neurological exam. An abbreviated PE will be performed on Day -1 (unless a complete PE was performed < 7 days before dosing) and Day 4. An abbreviated PE differs from a complete PE in that the

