14.3.5 Displays of Laboratory Results

14.3.5.1 Chemistry Results

Table 19: Chemistry Laboratory Results by Severity and Time Point – Any Chemistry Parameter

		None		Mild/ Grade 1		Moderate/ Grade 2		Severe/ Grade 3		Missing	
Time Point	N	n	%	N	%	n	%	N	%	n	%
Baseline	x	x	x	X	X	x	x	X	x	x	X
Day 4	x	x	x	X	X	x	x	X	x	x	X
Max Severity Post Baseline	x	x	x	X	X	x	x	X	x	x	X

Note: The “Max Severity Post Baseline” rows indicate the maximum severity experienced by each subject at any time point post baseline, including unscheduled assessments. N=Number of subjects in the Safety Population.

Table 20: Chemistry Laboratory Results by Severity and Time Point – Sodium

Time Point	N	None		Mild/ Grade 1 (Low)		Mild/ Grade 1 (High)		Moderate/ Grade 2 (Low)		Moderate/ Grade 2 (High)		Severe/ Grade 3 (Low)		Severe/ Grade 3 (High)		Missing	
		n	%	n	%	N	%	n	%	n	%	n	%	N	%	n	%
Baseline	x	x	x	x	x	X	x	x	x	x	x	x	x	X	x	x	x
Day 4	x	x	x	x	x	X	x	x	x	x	x	x	x	x	x	x	x
Max Severity Post Baseline	x	x	x	x	x	X	x	x	x	x	x	x	x	x	x	x	x

Note: The “Max Severity Post Baseline” rows indicate the maximum severity experienced by each subject at any time point post baseline, including unscheduled assessments. N=Number of subjects in the Safety Population.

Table 21: Chemistry Laboratory Results by Severity and Time Point – Potassium

This table will repeat Table 20 for Potassium.

Table 22: Chemistry Laboratory Results by Severity and Time Point – Bicarbonate

This table will repeat Table 20 for Bicarbonate.

Table 23: Chemistry Laboratory Results by Severity and Time Point – Glucose

This table will repeat Table 20 for Glucose.

Table 24: Chemistry Laboratory Results by Severity and Time Point – Blood Urea Nitrogen

This table will repeat Table 19 for Blood Urea Nitrogen.

Table 25: Chemistry Laboratory Results by Severity and Time Point – Creatinine

This table will repeat Table 19 for Creatinine.

Table 26: Chemistry Laboratory Results by Severity and Time Point – Protein

This table will repeat Table 19 for Protein.

Table 27: Chemistry Laboratory Results by Severity and Time Point – Albumin

This table will repeat Table 19 for Albumin.

Table 28: Chemistry Laboratory Results by Severity and Time Point – Aspartate Aminotransferase

This table will repeat Table 19 for Aspartate Aminotransferase.

Table 29: Chemistry Laboratory Results by Severity and Time Point – Alanine Aminotransferase

This table will repeat Table 20 for Alanine Aminotransferase.

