Table 55: Chemistry Laboratory Summary Statistics by Time Point – Aspartate Aminotransferase (U/L)

This table will repeat Table 45 for Aspartate Aminotransferase.

Table 56: Chemistry Laboratory Summary Statistics by Time Point – Alanine Aminotransferase (U/L)

This table will repeat Table 45 for Alanine Aminotransferase.

Table 57: Chemistry Laboratory Summary Statistics by Time Point – Alkaline Phosphatase (U/L)

This table will repeat Table 45 for Alkaline Phosphatase.

Table 58: Chemistry Laboratory Summary Statistics by Time Point – Bilirubin (mg/dL)

This table will repeat Table 45 for Bilirubin.

Table 59: Chemistry Laboratory Summary Statistics by Time Point – Direct Bilirubin (mg/dL)

This table will repeat Table 45 for Direct Bilirubin.

Table 60: Hematology Laboratory Results by Severity and Time Point – Any Hematology Parameter

This table will repeat Table 19 for Any Hematology Parameter.

Table 61: Hematology Laboratory Results by Severity and Time Point – Hemoglobin

This table will repeat Table 19 for Hemoglobin.

Table 62: Hematology Laboratory Results by Severity and Time Point – Leukocytes

This table will repeat Table 19 for Leukocytes.

Table 63: Hematology Laboratory Results by Severity and Time Point – Neutrophils

This table will repeat Table 19 for Neutrophils.

Table 64: Hematology Laboratory Results by Severity and Time Point – Lymphocytes

This table will repeat Table 19 for Lymphocytes.

Table 65: Hematology Laboratory Results by Severity and Time Point – Monocytes

This table will repeat Table 19 for Monocytes.

Table 66: Hematology Laboratory Results by Severity and Time Point – Eosinophils

This table will repeat Table 19 for Eosinophils.

Table 67: Hematology Laboratory Results by Severity and Time Point – Basophils

This table will repeat Table 19 for Basophils.

Table 68: Hematology Laboratory Results by Severity and Time Point – Platelets

This table will repeat Table 19 for Platelets.

Table 69: Hematology Abnormal Laboratory Results Related to Study Treatment by Severity and Time Point – Any Hematology Parameter

This table will repeat Table 32 for Any Hematology Parameter.

Table 70: Hematology Abnormal Laboratory Results Related to Study Treatment by Severity and Time Point – Hemoglobin

This table will repeat Table 32 for Hemoglobin.

Table 71: Hematology Abnormal Laboratory Results Related to Study Treatment by Severity and Time Point – Leukocytes

This table will repeat Table 32 for Leukocytes.

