This table will repeat Table 19 for Any Urinalysis Parameter.

Table 89: Urinalysis Laboratory Results by Severity and Time Point – Protein

This table will repeat Table 19 for Protein.

Table 90: Urinalysis Laboratory Results by Severity and Time Point – Glucose

This table will repeat Table 19 for Glucose.

Table 91: Urinalysis Laboratory Results by Severity and Time Point – Hemoglobin

This table will repeat Table 19 for Hemoglobin.

Table 92: Urinalysis Abnormal Laboratory Results Related to Study Treatment by Severity and Time Point – Any Urinalysis Parameter

This table will repeat Table 32 for Any Urinalysis Parameter.

Table 93: Urinalysis Abnormal Laboratory Results Related to Study Treatment by Severity and Time Point – Protein

This table will repeat Table 32 for Protein.

Table 94: Urinalysis Abnormal Laboratory Results Related to Study Treatment by Severity and Time Point – Glucose

This table will repeat Table 32 for Glucose.

Table 95: Urinalysis Abnormal Laboratory Results Related to Study Treatment by Severity and Time Point – Hemoglobin

This table will repeat Table 32 for Hemoglobin.

14.3.6 Displays of Vital Signs**Table 96: Vital Signs by Assessment, Maximum Severity, and Time Point – Any Assessment**

This table will repeat Table 19 for Vital Signs – Any Assessment.

Table 97: Vital Signs by Assessment, Maximum Severity, and Time Point – Systolic Blood Pressure

This table will repeat Table 20 for Vital Signs – Systolic Blood Pressure.

Table 98: Vital Signs by Assessment, Maximum Severity, and Time Point – Diastolic Blood Pressure

This table will repeat Table 19 for Vital Signs – Diastolic Blood Pressure.

Table 99: Vital Signs by Assessment, Maximum Severity, and Time Point – Pulse Rate

This table will repeat Table 20 for Vital Signs – Pulse Rate.

Table 100: Vital Signs by Assessment, Maximum Severity, and Time Point – Respiratory Rate

This table will repeat Table 19 for Vital Signs – Respiratory Rate.

Table 101: Vital Signs by Assessment, Maximum Severity, and Time Point –Temperature

This table will repeat Table 19 for Vital Signs – Temperature.

Table 102: Vital Signs Summary Statistics by Assessment and Time Point – Systolic Blood Pressure (mmHg)

Time Point	N	Mean	Standard Deviation	Median	Min, Max
Baseline					
1 h (± 10 min) after dosing					
1 h, Change from Baseline					
2 h (± 10 min) after dosing					
2 h, Change from Baseline					
4 h (± 10 min) after dosing					
4 h, Change from Baseline					
Day 2					

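### SAP 9.6 and 9.7 do not limit the count-twice tie rule to tables with Low and High columns; read literally, one subject can be entered twice in the same undirected grade cell

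*SAP*

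**What the plan says.** SAP 9.6 introduces the roll-up tables: "Tables of maximum severity for “Any Parameter” will be included for chemistry, hematology, and urinalysis laboratory results". The same paragraph then gives the counting rule: "Ordinarily, only the maximum severity event will be counted in the summary tables". Its example is a subject with a mild decrease and a moderate increase, who is counted once as a moderate increase. For a tie the rule changes: if "a subject has an increase and a decrease of equal maximum severity, they will be counted twice for maximum severity post baseline", the two entries are made "once for an increase and once for a decrease".

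SAP 9.7 does the same for vital signs. It describes the Any Parameter table ("In these tables, the maximum severity across all VS is summarized by visit, and from maximum severity post baseline") and then repeats the tie rule.

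The table shells in SAP Appendix 1 are of two kinds:

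- **Directed.** Table 20 (sodium) and Table 33 (related sodium results) split each grade into Low and High. Other tables copy them, including systolic pressure (97) and pulse rate (99).
- **Undirected.** Table 19 (Any Chemistry Parameter) has None, Grade 1, Grade 2, Grade 3 and Missing. Table 32, its related-only counterpart, has the three grades alone. Table 60 says "This table will repeat Table 19 for Any Hematology Parameter" and Table 96 says "This table will repeat Table 19 for Vital Signs". Table 62 (leukocytes) also copies Table 19; Tables 69 and 71 copy Table 32.

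The Table 19 footnote says that the maximum-severity "rows indicate the maximum severity experienced by each subject at any time point post baseline". N is the number of subjects in the Safety Population.

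**The concern.** The rule works in a directed shell: the two entries go into two different cells, one Low and one High. An undirected shell offers only one cell per grade, so both entries land in it. The rule follows directly on the description of the Any Parameter tables and makes no exception for them.

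For laboratory data, those tables are also where a tie is most likely to occur. Day 4 (or early termination) is the only scheduled post-dose draw, so one analyte cannot be both high and low without an extra test, whereas two analytes can point in opposite directions in a single sample.

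At stake is a subject count in the roll-up safety tables of an eight-subject trial, where one extra entry is visible in the percentage. The AE summaries count each subject once per category (SAP 9 and 9.3), so the two sets of tables could disagree about the same findings.

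**Working it through.** The documents give no figure on this point, so there is none to reproduce. The check has three steps.

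**1. Can a tie occur in an undirected shell?** The grading limits are in SAP Tables 3 and 4 (Protocol Appendix C).

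- Any Chemistry (19): on Day 4, fasting glucose 108 mg/dL is Grade 1 high (107 to 125) and albumin 3.4 g/dL is Grade 1 low (2.8 to 3.4). Both are in the severity list of SAP 9.6. In Table 32 both must also be judged related.
- Any Hematology (60, 69): eosinophils, monocytes and basophils are graded for increases; hemoglobin, neutrophils, lymphocytes and platelets for decreases; WBC for both. Opposite findings in one sample are possible.
- Any Vital Sign (96): systolic 142 mmHg at 2 h is Grade 1 (141 to 150). Pulse 53 on Day 3, with a baseline of at least 60, is Grade 1 (50 to 54).
- Leukocytes (62, 71): WBC is graded both ways, but a tie within one analyte needs a second post-dose sample. SAP 9.6 keeps unscheduled tests out of the tables; the Table 19 footnote includes them in the maximum row. These tables are affected only if the footnote governs.
- Any Urinalysis (88, 92): every urine grade is an increase, so no tie can arise.

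**2. Size of one tie.** Inputs: N = 8 (SAP 5), and k = the number of other subjects already in the cell.

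- Counted once: (k+1)/N
- Counted twice: (k+2)/N
- Difference: 1/N = 1/8 = 12.5 points
- Ratio: (k+2)/(k+1)

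| k | Counted once | Counted twice | Ratio |
|---|---|---|---|
| 0 | 1/8 = 12.5% | 2/8 = 25.0% | 2.00 |
| 1 | 2/8 = 25.0% | 3/8 = 37.5% | 1.50 |
| 3 | 4/8 = 50.0% | 5/8 = 62.5% | 1.25 |
| 7 | 8/8 = 100.0% | 9/8 = 112.5% | 1.125 |

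**3. Row total.** In Tables 19, 60, 62 and 96 the None, grade and Missing columns should account for everyone, so the row should sum to N. With one tie it sums to (N+1)/N = 9/8 = 112.5%. Tables 32, 69 and 71 have no None or Missing column, so they carry the extra count without a row total to expose it.

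The Safety Population may not be exactly 8. As an assumed range, N = 7 gives +14.3 points and a row total of 8/7 = 114.3%; N = 10 (eight plus the two alternates) gives +10 points and 11/10 = 110%.

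**The case against.** The strongest reply is that the rule was written with directed tables in mind. Making one entry per direction, and filing the example subject as a moderate increase, can only be done where direction columns exist. SAP 9.6 describes the Any Parameter tables as showing the maximum across all results in the category, which is a single value, and the Table 19 footnote agrees. A programmer who follows the footnote would count once.

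That reading is plausible and may well be what was intended. But the SAP does not state it, and the rule stands in the same paragraph as the tables it does not fit. The once-per-subject convention in SAP 9 and 9.3 governs AE incidence, not these tables.

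It is also fair to say that an error would often be noticed. The tie rule applies only to the maximum-severity row, so a Day 4 tie in Table 19 would show eight subjects in the Day 4 row and nine in the row below. By-subject listings and the AE tables would still be right. This limits the harm but does not settle what the rule means.

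A reader might infer three stronger things that the documents do not support:

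- **That the percentage always doubles.** It does so only when k = 0.
- **That every Any Parameter table is exposed.** The urinalysis tables are not.
- **That a rate of double counting can be quoted.** The documents give no means, standard deviations or correlations for laboratory values or vital signs, so any rate would rest on assumed distributions. For vital signs it would also depend on the repeat-measurement rule in Protocol 8.1.6 and the concordance comment in Appendix C. The SAP itself treats the tie as exceptional.

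**Conclusion.** The point holds as a conflict between a stated rule and the shells it is applied to. Read literally, SAP 9.6 and 9.7 enter one subject twice in one grade cell of Tables 19, 32, 60, 69 and 96, and of Tables 62 and 71 if unscheduled tests are counted. Each tie adds 1/N to the cell, 12.5 points if the Safety Population is 8, and contradicts the footnote's single maximum per subject.

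It would go too far to say that a double count is certain: that depends on how the programmer resolves the conflict and on a tie occurring. The effect is confined to descriptive safety tables. No PK endpoint or halting criterion uses these cells, and the trial tests no hypothesis. This is a low-priority correction.

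**What to change.** In SAP 9.6 and 9.7, limit the double count to tables with separate Low and High columns (the Table 20 and Table 33 shells). Add that in all undirected tables (the Table 19 and Table 32 shells) each subject is counted once, at the highest grade in either direction. This also covers leukocytes, whichever way the handling of unscheduled tests is settled.

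The cost is about one sentence in each of the two sections and one programming condition. No new data are needed.

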9.7. Vital Signs and Physical Evaluations

VS measurements include systolic blood pressure, diastolic blood pressure, pulse rate, respiratory rate, and oral temperature. VS will be assessed within 60 min of dosing (baseline), 1 h (± 10 min), 2 h (± 10 min), and 4 h (± 10 min) after dosing, and at Day 2, Day 3, Day 4, and Day 8 or ET. VS will be tabulated by parameter, severity grading, and visit (Table 96, Table 97, Table 98, Table 99, Table 100, and Table 101) and listed (Listing 15). Additionally, descriptive statistics, including mean, standard deviation, median, minimum and maximum will be presented to summarize VS at baseline and post-dose and will also present change from baseline (Table 102, Table 103, Table 104, Table 105 and Table 106). For each vital sign, individual line plots showing the vital sign over time will be shown by parameter (Figure 28, Figure 29, Figure 30, Figure 31 and Figure 32). Subjects will not be labeled in the line plots, as the purpose of the figures is to give an overall trend of trajectory.

In tables of severity, maximum severity observed for the parameter after dosing will be summarized. Tables of maximum severity for “Any Parameter” will be included for VS results. In these tables, the maximum severity across all VS is summarized by visit, and from maximum severity post baseline. Ordinarily, only the maximum severity event will be counted in the summary tables. For instance, if subject has a mild decrease and a moderate increase observed post-dose, they will be counted once as a moderate increase for maximum severity post-baseline. In the exceptional case that a subject has an increase and a decrease of equal maximum severity, they will be counted twice for maximum severity post baseline, once for an increase and once for a decrease.

A complete physical examination (PE), except genital, rectal and breast exams, will be conducted at Screening and at Day 8 (± 2) or ET. This examination will assess general appearance, HEENT (head, eyes, ears, nose and throat), heart, lungs, abdomen, skin, musculoskeletal system, and lymph nodes, and include an abbreviated neurological exam. An abbreviated PE will be performed on Day -1 (unless a complete PE was performed < 7 days before dosing) and Day 4. An abbreviated PE differs from a complete PE in that the

abdomen and neurological system are not evaluated. A symptom-directed PE will be performed before dosing on Day 1 and after dosing on Days 1, 2, and 3, to evaluate new symptoms or treatment-emergent AEs, respectively. Results of physical examinations, scheduled and unscheduled, will be presented in Listing 16.

9.8. Concomitant Medications

All medications will be coded using the current version of the WHO Drug dictionary. The use of prior and concomitant medications taken during the study will be summarized by ATC 1 and ATC 2 (separately in [Table 117](#) for prior medications and [Table 118](#) for concomitant medications). Individual subject listings will be presented for all prior and concomitant medications (separately in [Listing 18](#) for prior medications and [Listing 19](#) for concomitant medications).

9.9. Other Safety Measures

A 12-lead ECG and 10-sec rhythm strip will be obtained at Screening Visit and on Days -1, 1, and 4 (72 h \pm 2 h post dose), or ET. On Day 1, a 12-lead ECG and 10-sec rhythm strip will be recorded within 1 h before dosing and 1 h (\pm 10 min), 2 h (\pm 10 min), and 4 h (\pm 10 min) after dosing. ECG change in overall interpretation from baseline will be shown by study visit in [Table 107](#). For PR interval and QT intervals with Fridericia correction (QTcF), ECG results will be tabulated by parameter, severity grading, and visit ([Table 108](#) and [Table 109](#)). Summary statistics of ECG results, including change from baseline, will be reported by parameter (PR interval, QRS duration, QT interval, QTcF interval, RR interval, and ECG mean ventricular rate) in tabular form by study visit ([Table 110](#), [Table 111](#), [Table 112](#), [Table 113](#), [Table 114](#), and [Table 115](#)) and will be shown graphically as line plots by visit ([Figure 33](#), [Figure 34](#), [Figure 35](#), [Figure 36](#), [Figure 37](#), [Figure 38](#), and [Figure 39](#)). Subjects will not be labeled in the line plots, as the purpose of the figures is to give an overall trend of trajectory. Line plots of change from baseline will be shown for QTcF intervals ([Figure 37](#)) but change from baseline will not be shown graphically for other ECG parameters. Frequency of QTcF prolongation (between 30 and <60 msec or \geq 60 msec) will be given by post-dose visit ([Table 116](#)). Individual data listings of ECG results (interpretation, PR interval, QRS duration, QT interval, QTcF interval, RR interval, and ECG mean ventricular rate) will be presented ([Listing 17](#)).

10. PHARMACOKINETICS

The PK analysis plan is described in the PK SAP. The summary from the PK Report and key tables, figures and listings (concentrations, parameters, and mean time-concentration profiles) will be included in the CSR.

11. IMMUNOGENICITY

There are no immunogenicity endpoints in this trial.

12. OTHER ANALYSES

There are no other analyses in this trial.

13. REPORTING CONVENTIONS

P-values ≥ 0.001 and ≤ 0.999 will be reported to 3 decimal places; p-values < 0.001 will be reported as “ < 0.001 ”; p-values > 0.999 will be reported as “ > 0.999 ”. All summary statistics besides the minimum value and maximum value will be reported to 1 decimal place greater than the original data. The minimum and maximum will use the same number of decimal places as the original data. Proportions will be presented as 2 decimal places; proportions > 0 but < 0.01 will be presented as “ < 0.01 ”. Percentages will be reported to the nearest whole number; percentages > 0 but $< 1\%$ will be presented as “ < 1 ”.

